4.2 Registration Process for DF/HCC and DF/PCC Institutions

5. TREATMENT PLAN

Treatment will be administered on an outpatient or inpatient basis. Expected toxicities and potential risks as well as dose modifications for ixazomib, rituximab, and dexamethasone are described in Section 6 (Expected Toxicities and Dosing Delays/Dose Modification). No investigational or commercial agents or therapies other than those described below may be administered with the intent to treat the participant’s malignancy.

IDR Induction Phase					
Agent	Premedications	Dose	Route	Schedule	Cycle Length
Dexamethasone	None	20 mg	IV or PO	Days 1, 8, 15 Before ixazomib and rituximab	Every 4 weeks for Cycles 1-6 Rituximab omitted from cycles 1 and 2
Ixazomib	None	4 mg	PO	Days 1, 8 15 After dexamethasone	
Rituximab	Diphenhydramine 25-50 mg PO/IV Acetaminophen 650-1000 mg PO Famotidine 20mg IV	375 mg/m ²	IV infusion	Day 1 After Ixazomib	

IDR Maintenance Phase					
Agent	Premedications	Dose	Route	Schedule	Cycle Length

CONFIDENTIAL

This document is confidential. Do not disclose or use except as authorized.

Dexamethasone	None	20 mg	IV or PO	Day 1, 8, and 15 Before Ixazomib and Rituximab	Every 8 weeks +/- 2 weeks for Cycles 1-6
Ixazomib	None	4 mg	PO	Day 1, 8, and 15 After Dexamethasone	
Rituximab	Diphenhydramine 25-50 mg PO/IV Acetaminophen 650-1000 mg PO Famotidine 20mg IV	375 mg/m ²	IV infusion	Day 1 After Ixazomib	

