10.4 Time to Progression

Time to Progression (TTP) is defined as the duration of time from start of treatment to time of disease progression as defined in section 10.1. Death from any cause or initiation of a new anti-neoplastic therapy will also be considered a progression event.

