10.5 Time to Next Therapy

Time to Next Therapy (TNT) is defined as the duration from start of protocol treatment to time of initiation of any new anti-neoplastic therapy, including radiation or intrathecal therapy.

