14.2 Populations for analysis

The population for all safety analyses is the Safety Analysis Set (SAS). All participants who receive at least one dose of any test material during the study will be included in the SAS population and included in the safety analysis.

Participants will be included in the Full Analysis Set (FAS) for the primary assessment of efficacy. The FAS will include those participants who have measurable disease present at baseline, have received at least one cycle of therapy, and have had their disease re-evaluated.

CONFIDENTIAL

This document is confidential. Do not disclose or use except as authorized.

The Per-Protocol Analysis Set (PPS) is defined as all participants from the FAS set who complete the study and are deemed to be protocol-compliant. To be protocol-compliant, a participant must not have any major protocol deviations during the study period. Protocol deviations will be identified prior to database lock and will be listed in the clinical study report. The PPS will be used for a secondary assessment of efficacy endpoints.

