14.7 Efficacy Analyses

Primary and secondary analyses will be performed in both the FAS and PPS populations and will include calculating the proportion of patients having an overall response (MR or better) and major response (CR or VG). Confidence intervals (95%) about these point estimates will be presented. Time to progression (TTP) and time to next therapy (TNT) as defined in sections 10.4, and 10.5, respectively will be estimated using Kaplan and Meier methodology with median time plus 25th and 75th percentile time to progression free survival along with 95% confidence intervals being provided, as appropriate. In addition, landmark analysis for 2 and 4 year progression free survival will be performed.

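### The per-protocol set's undefined study-completion condition most naturally drops on-treatment progressors, which biases its time-to-progression and time-to-next-therapy estimates upward

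*Combined protocol and SAP*

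**What the plan says.** Section 14.2 defines three sets. The full analysis set (FAS) is primary for efficacy. It takes participants with measurable disease at baseline who "have received at least one cycle of therapy, and have had their disease re-evaluated". The PPS is cut from it: "The Per-Protocol Analysis Set (PPS) is defined as all participants from the FAS set who complete the study and are deemed to be protocol-compliant". Compliance is then explained as having no major deviation, but completion is not explained. On use, 14.2 adds: "The PPS will be used for a secondary assessment of efficacy endpoints".

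Section 14.7 opens: "Primary and secondary analyses will be performed in both the FAS and PPS populations". It then specifies Kaplan-Meier estimates of TTP and TNT as defined in 10.4 and 10.5, and adds that "landmark analysis for 2 and 4 year progression free survival will be performed", naming neither a population nor a time origin for PFS. Section 10 does not define PFS.

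The clocks are explicit. Section 10.4: "Time to Progression (TTP) is defined as the duration of time from start of treatment to time of disease progression", with death and new anti-neoplastic therapy also counted as events. Section 10.5: "Time to Next Therapy (TNT) is defined as the duration from start of protocol treatment", ending when any new anti-neoplastic therapy begins. Section 5 says of the treatment period: "No investigational or commercial agents or therapies other than those described below may be administered" to treat the malignancy.

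**The concern.** Completion is a second filter on top of compliance, so it must exclude someone who has no major deviation. The protocol's own usage suggests who that is. Section 5.4 ends therapy after 6 induction and 6 maintenance cycles or earlier on listed criteria, of which progression is the first. Section 5.6 takes anyone meeting such a criterion off the study, not merely off treatment. Section 7.5 lists progressive disease as a reason for withdrawal from the study. The calendar treats finishing all treatment and being removed from the trial as alternatives. Section 14.3 sets completers against premature discontinuations.

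If progressors on treatment are non-completers, membership of the PPS depends on the outcome being analysed. Time from treatment start to the end of treatment becomes immortal time. A reader comparing PPS and FAS curves would attribute to protocol adherence a difference that the set definition creates.

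**Working it through.** The plan states no PPS estimate, so there is no published figure to reproduce. What can be checked is the length of the event-free window and the shift it produces.

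**1. Length of the window.** Section 1.1 gives 24 weeks of induction and 52 of maintenance: 24 + 52 = 76 weeks. The visit schedule agrees: induction cycle 6 day 1 is week 5 × 4 = 20, maintenance starts 8 weeks later at week 28, and 28 + 6 × 8 = 76. In months, T = 76 × 7 / 30.44 = 17.48. If completion means the last planned dose, that is day 15 of maintenance cycle 6: 28 + 5 × 8 + 2 = week 70, or 70 × 7 / 30.44 = 16.10 months.

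**2. Direction.** Let S(t) be event-free survival from treatment start in all treated participants. Restricting to those event-free at T gives 100% up to T and S(t)/S(T) afterwards. Since S(T) ≤ 1, S(t)/S(T) ≥ S(t) for any curve. For TNT, new therapy is barred during protocol treatment, so a TNT event before T also implies early removal.

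**3. Size at 2 years.** Assumption: S(t) = 2^(−(t/m)^k), with median m and Weibull shape k. The only benchmark in the documents is the PFS of more than 56 months quoted in 2.3 for a bortezomib-based regimen. I use m = 56 and, as an unsourced assumption, m = 80, with k = 0.7, 1 and 1.5. Example for m = 56, k = 1: S(24) = 2^(−24/56) = 74.3%; S(17.48) = 80.5%; ratio = 92.2%; gap = 17.9 points.

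| m (months) | k | All treated, S(24) | Event-free at T, S(24)/S(T) | Gap, T = 17.48 | Gap, T = 16.10 | Expected exclusions, 26 × (1 − S(17.48)) |
|---|---|---|---|---|---|---|
| 56 | 0.7 | 68.2% | 92.7% | 24.5 | 22.9 | 6.9 |
| 56 | 1 | 74.3% | 92.2% | 17.9 | 16.4 | 5.1 |
| 56 | 1.5 | 82.3% | 92.9% | 10.6 | 9.3 | 3.0 |
| 80 | 0.7 | 74.2% | 94.2% | 20.0 | 18.8 | 5.5 |
| 80 | 1 | 81.2% | 94.5% | 13.3 | 12.2 | 3.7 |
| 80 | 1.5 | 89.2% | 95.8% | 6.5 | 5.8 | 1.8 |

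In whole participants: if 3 of 26 progress on treatment and 2 more by 2 years, the rate is 21/26 = 81% in all 26 and 21/23 = 91% after the exclusion.

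**4. Could other exclusions cancel this?** Suppose a fraction d leaves early for reasons other than an event, with 2-year PFS q, and everyone else follows S. No bias at 2 years requires q = [S(24)/S(T) − (1 − d) × S(24)] / d. With m = 56, k = 1 and d = 0.3, q = (0.922 − 0.7 × 0.743) / 0.3 = 1.34, which is impossible. With d = 0.1 it is 2.54. So for d between 0.1 and 0.3 on this curve, such exits cannot cancel the upward shift.

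**5. Would it show?** Under 1.1 the final analysis falls when all participants would have finished maintenance. Anyone enrolled at least 24 − 17.5 = 6.5 months before the last participant has 2 years of follow-up by then, so a 2-year contrast would appear if accrual takes the planned 12 to 15 months. I make no 4-year or median contrast.

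**The case against.** The reading is an inference. Section 5.4 makes progression one of the protocol's own end points of therapy, so a participant treated to progression has arguably finished the study as designed. Section 5.5 describes follow-up after removal from study and so seems to count treatment completers as removed too; removal alone does not prove non-completion. Completion could also mean finishing follow-up, which 5.5 ends at next therapy or death, so a progressor could qualify. With progressors counted as completers, the bias described here does not arise.

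A reader might infer that the follow-up reading is impossible. A treatment completer would need (76 + 104) × 7 / 30.44 = 41.4 months, while planned accrual of 12 to 15 months gives at most 29.5 to 32.5 months at the final analysis. But the accrual figure is in 14.8, which describes 33 participants rather than the 26 of 14.1. Accrual of about 24 months (41.4 − 17.5 = 23.9) would be enough for the earliest completers, and 14.7 plans a 4-year PFS that the same timing could not supply. The timing weighs against that reading but does not exclude it.

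The size also rests on assumptions. The 56-month figure is a lower bound from another regimen, and the largest gap needs an early-peaking hazard that nothing in the documents supports. The comparator is all treated participants; the FAS already drops those without a cycle of therapy or a re-evaluation, so the PPS-to-FAS gap may differ slightly.

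Finally, a reader might infer that the trial's conclusion is compromised. It is not: the FAS is primary, success is a response count under 14.1, and 14.3 requires completed and discontinued numbers with reasons, so the exclusions would be visible. What stands is that an undefined condition, on its most natural reading, selects a set on its own outcome, and no shifted origin, left truncation or exemption for progressors is given.

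**Conclusion.** The point holds conditionally. If completion means finishing the planned treatment, which is the most natural but not the only reading, PPS estimates of TTP and TNT are biased upward because members are event-free for about 17.5 months by construction. The 2-year PFS figure is affected in the same way only if it is run in the PPS and timed like TTP; the plan states neither. The direction of the event-based selection does not depend on the curve. The size does: about 6 to 25 points at 2 years (5.8 to 24.5) against all treated participants, for assumed medians of 56 to 80 months and Weibull shapes 0.7 to 1.5. No size can be given for TNT because the documents give no TNT rate. This is a minor-to-moderate correction to a secondary analysis; the primary VGPR-or-better result and the rule of at least 9 responders do not change.

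**What to change.** In 14.2, delete the condition that PPS members complete the study. Define the PPS as FAS participants with no major protocol deviation, and state that progression, death and withdrawal for toxicity are not deviations. PPS time-to-event analyses can then stay without a separate restriction.

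In 14.7, make the FAS (or all dosed participants) the main set for TTP, TNT and PFS, and state the population and time origin for PFS.

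The cost is two or three sentences of SAP wording, with no new data and no change to the primary set or the success rule. Section 14.1 reports 27 participants already accrued, including one who never started, so the date of the change should be documented. The documents do not say whether the final analysis has been done; if it has, the change should be labelled post hoc.

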14.3 Participant Disposition

The total number of participants screened, completed, and prematurely discontinued from the study will be summarized. The reason for termination for all participants who discontinued will also be presented. A listing of participants with major protocol deviations will also be presented.

14.4 Participants Baseline Characteristics

Descriptive summaries of demographic and baseline characteristics will be presented for all participants.

14.5 Exposure to Investigational Material

Exposure to all test material will be tabulated by presenting number of days on study, defined as number of days from day of first dose to day of last infusion. Total amount of investigational material taken will also be presented.

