5.2.1.3 Ixazomib Administration

Ixazomib should be administered after dexamethasone each and every cycle, unless dexamethasone is omitted. Please refer to section 2.1.3.3. The order of administration should be dexamethasone followed by ixazomib followed by rituximab.

All protocol-specific criteria for administration of study drug must be met and documented before drug administration. Study drug will be administered or dispensed only to eligible patients under the supervision of the investigator or identified sub-investigator(s). Patients should be monitored for toxicity, as necessary, and doses of **ixazomib** should be modified as needed to accommodate patient tolerance to treatment; this may include symptomatic treatment, dose interruptions, and adjustments of **ixazomib** dose (see Section 6.2).

Capsules of **ixazomib** will also be referred to as study drug. Study drug will be supplied by Millennium as capsules of 2.3, 3.0 and 4.0 mg **ixazomib**. The prescribed administration of **ixazomib** doses in this study is 4 mg **ixazomib** PO once weekly (+/-3 days) on days 1, 8 and 15 in a 28-day cycle during induction therapy, and once on days 1, 8, and 15 in each maintenance cycle.

Patients should be instructed to swallow **ixazomib** capsules whole, with water, and not to break, chew, or open the capsules. Study drug should be taken on an empty stomach (no food or drink) at least 1 hour before or 2 hours after a meal. Each capsule should be swallowed separately with a sip of water. A total of approximately 8 ounces (240 mL) of water should be taken with the capsules.

Missed doses can be taken as soon as the patient remembers if the next scheduled dose is 72 hours or more away. A double dose should not be taken to make up for a missed dose. If the patient vomits after taking a dose, the patient should not repeat the dose but should resume dosing at the time of the next scheduled dose.

Ixazomib drug product is an anti-cancer drug. Refer to the published institutional guidelines regarding the proper handling and disposal of anti-cancer agents.

Investigational **ixazomib** (expired or end of study) should be destroyed on site according to the institution's standard operating procedure. Be sure to document removal and destruction on drug

CONFIDENTIAL

This document is confidential. Do not disclose or use except as authorized.

accountability logs.

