5.2.2.6 Rituximab Treatment Schedule and Administration

CONFIDENTIAL

This document is confidential. Do not disclose or use except as authorized.

Rituximab should be administered after ixazomib on day 1 of induction cycles 3-6 and maintenance cycles 1-6. The order of administration should be dexamethasone followed by ixazomib followed by rituximab. Please see section 5.2.1.3.

During the induction phase Cycles 3-6 on Day 1 and the maintenance phase Cycles 1-6 on Day 1, Rituximab 375 mg/m² IV is to be administered at an initial rate of 50 mg/hour for the first hour then escalate the rate in 50 mg/ hours increments approximately every 30 minutes, to a maximum of 400 mg/hour. If hypersensitivity or an infusion-related event develops such as T>101.3, mucosal edema, or a >30mm Hg decrease in SBP, interrupt the infusion, administer hypersensitivity rescue medications. When symptoms have resolved, the infusion can continue at one-half the previous rate and escalate in 50 mg/hr increments approximately each half hour, as tolerated. The infusion may be discontinued early at the discretion of the treating investigator. For patients who have tolerated previous infusions without hypersensitivity, subsequent infusions can be administered at an initial rate of 100 mg/hr, and increased by 100 mg/hr increments at approximately 30-minute intervals, to a maximum of 400 mg/hr as tolerated. Alternatively, subsequent infusions can be administered at an initial rate of 20 percent of the total dose over 30 minutes, followed by the remaining 80 percent of the total dose over 60 minutes.

Vital signs: At the first infusion, vital signs should be checked and recorded at baseline, at the first rate change (usually at the approximately 1 hour point), as needed for signs and symptoms of hypersensitivity reaction, and at the end of the infusion. For subsequent infusions, vitals should be taken at baseline, and as needed for signs or symptoms of a reaction.

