5.2.2.9 Modification of Rate for Infusion of Rituximab

CONFIDENTIAL

This document is confidential. Do not disclose or use except as authorized.

In the event that patients develop an infusion related or hypersensitivity reaction to rituximab then the rate of drug administration is altered as described above. The total dose administered remains the same in such cases. In the event of serious or life threatening reactions, the infusion should be terminated and such adverse events reported. In the event of serious or life threatening events attributed to rituximab, patients may permanently discontinue rituximab and remain on the study after consultation with the overall PI.

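### Section 14.5 ends exposure at the last infusion although ixazomib is oral and rituximab can stop alone, so recorded duration is 14 days short for a completer on oral day 8 and 15 dexamethasone, and otherwise depends on steroid route

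*Combined protocol and SAP*

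**What the plan says.** Section 14.5 sets a single time-on-study measure covering every study material, and gives its limits as follows: "defined as number of days from day of first dose to day of last infusion". A separate sentence promises a quantity as well: "Total amount of investigational material taken will also be presented". No other section redefines when exposure ends.

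The regimen to which this applies:

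- **Ixazomib** (5.2.1.3) is given "PO once weekly (+/-3 days) on days 1, 8 and 15 in a 28-day cycle during induction therapy". The same three dosing days apply to every maintenance cycle.
- **Rituximab** (5.2.2.6): "Rituximab should be administered after ixazomib on day 1 of induction cycles 3-6 and maintenance cycles 1-6". The induction table in Section 5 notes: "Rituximab omitted from cycles 1 and 2".
- **Stopping rituximab alone.** For serious or life-threatening events, 5.2.2.9 says that "patients may permanently discontinue rituximab and remain on the study after consultation with the overall PI". Section 6.2.1.5 separately lets patients who cannot tolerate rituximab continue the rest of the protocol therapy.
- **Dexamethasone** may be intravenous or oral (1.1, Section 5, 5.2.3.3). It may be oral on days 8 and 15 when taken outside the clinic (5.2.3.3, 7.3.5). It may be omitted without taking the patient off study treatment (2.1.3.3).

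**The concern.** The start of the interval is a dose and its end is an infusion. The investigational drug is never infused, so the end point is set by whichever companion drug happens to go in by vein. Three things follow if the sentence is programmed as written. Ixazomib taken after the last infusion is not counted. A patient who drops rituximab early may stop accruing days while still on ixazomib. A patient who leaves early may have no end date at all.

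The toxicity profile is a primary objective (1.2). Readers will judge the adverse event tables against how long patients were treated, and 14.5 is the plan's only statement of that duration.

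**Working it through.** The plan gives no numerical exposure figure to reproduce. One input can be checked: 6 cycles x 28 days = 168 days = 24 weeks, which matches the induction duration in 1.1.

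**Nominal calendar**, with first dose = day 1, 28-day induction cycles, maintenance starting 8 weeks after induction cycle 6 day 1, and 8-week maintenance cycles (1.1, Section 5, Section 9):

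- First rituximab, induction cycle 3 day 1: 2 x 28 + 1 = day 57
- Fourth rituximab, induction cycle 6 day 1: 5 x 28 + 1 = day 141
- Maintenance cycle 1 day 1: 141 + 56 = day 197
- Ninth rituximab, maintenance cycle 5 day 1: 197 + 4 x 56 = day 421
- Tenth and last rituximab, maintenance cycle 6 day 1: 197 + 5 x 56 = day 477
- Last ixazomib, maintenance cycle 6 day 15: 477 + 14 = day 491

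**Shortfall = 491 minus day of last infusion**, where only rituximab is infused, or counted as infused, from the last rituximab onward and ixazomib is completed:

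| Last rituximab | Recorded day | Shortfall | Share of 491 |
|---|---|---|---|
| Infusion 10 (completer) | 477 | 14 | 2.9% |
| Infusion 9 | 421 | 70 | 14.3% |
| Infusion 4 | 141 | 350 | 71.3% |
| Infusion 1 | 57 | 434 | 88.4% |

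Counting elapsed days instead (490 in total) leaves the gaps unchanged and moves the last percentage to 88.6%.

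**Off treatment before cycle 3.** Six ixazomib doses are scheduled before any rituximab, the last on cycle 2 day 15: 28 + 15 = day 43. With only oral or omitted dexamethasone there is no infusion, so the duration is undefined.

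**Effect of steroid route.** If intravenous dexamethasone counts as an infusion:

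- Given intravenously on day 1 of each cycle and orally on days 8 and 15: last infusion day 477, shortfall 14 days, even if rituximab stopped early.
- Given intravenously on every ixazomib day: last infusion day 491, shortfall 0.

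Two patients with identical ixazomib dosing who both stop rituximab after infusion 1 could therefore be recorded at 57 or 491 days because of steroid route alone.

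**Sensitivity to the calendar.** Section 1.1 words the maintenance interval as 2 months. At 60.9 days per interval, the last infusion falls 140 + 6 x 60.9 = 505.4 days after first dose and the last ixazomib dose at 519.4. The completer gap stays at 14 days and the worst case becomes 519.4 - 56 = 463.4 days.

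**Scale in the summary.** Section 14.1 reports 27 accrued, one of whom never started, so 26 treated. One worst-case patient lowers the mean duration by 434 / 26 = 16.7 days.

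**The case against.** The best defence is that this is a drafting slip that an analyst would read through. Section 7.3.5 speaks of infusions of ixazomib, a capsule, so the protocol uses the word loosely, and last infusion may simply mean last dose. That is plausible as to intent. But 14.5 uses dose for the start and infusion for the end in the same phrase, and nothing tells the analyst to treat them as the same.

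A second defence is that 7.3.5 presents intravenous dexamethasone as the standard route, with oral substitution in a supply shortage or on days 8 and 15 outside the clinic. If intravenous steroid counts, the large shortfalls disappear. This part stands: the 434-day figure and the undefined case are conditional. It does not rescue the definition, because 1.1, Section 5 and 5.2.3.3 allow either route and 14.5 does not say whether a steroid infusion counts. The maintenance dexamethasone schedule is itself inconsistent (5.2.3.3 gives day 1 of cycles 1-8; 1.1, Section 5 and Section 9 give days 1, 8 and 15 over six cycles) and must be reconciled.

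Third, the total amount taken will also be reported, so continued ixazomib would show there. True, but an amount does not supply a duration.

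A reader might infer that the error inflates exposure-adjusted adverse event rates in rituximab-intolerant patients. The documents do not support that: 14.6 plans incidence, intensity and type of events, with tabulation by maximum severity, and no planned rate uses days of exposure as its denominator. The distortion would arise only if someone later computed such a rate from this variable.

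**Conclusion.** The definition does not fit the regimen and should be corrected. For a completer on oral dexamethasone on days 8 and 15, the loss is 14 of 491 days, about 3%. Larger losses, from 70 to 434 days at nominal timing, need three conditions together: rituximab stops before its last planned infusion, ixazomib continues to the end of maintenance, and no later intravenous dexamethasone is given or counted. The undefined case needs departure before cycle 3 with no intravenous steroid given or counted. The documents give no frequency for any of these, so 434 days is a worst case for one patient and should not be read as typical.

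The possibility of continuing without rituximab does not rest on 5.2.2.9 alone. Section 6.2.1.6 says patients with serious rituximab events may be removed from the study, which must be reconciled with 5.2.2.9, but 6.2.1.5 independently provides for continuing the other drugs.

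What is affected is a descriptive summary used to interpret the toxicity profile. The adverse event incidences and the VGPR decision rule do not depend on it.

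**What to change.** In 14.5, end overall exposure at the last dose of any study drug instead of the last infusion, and add duration for each of ixazomib, rituximab and dexamethasone from first to last dose of that drug. Keep the total amount taken, reported by drug. Doses taken against doses planned would be a useful addition, but the correction does not depend on it.

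The cost is a sentence or two of text and a small programming change, with no new visit and no change to treatment. This assumes that the per-cycle Treatment Form listed in 12.1.2 records dose dates for each drug; the protocol gives the form's submission deadline but not its fields, so this should be confirmed.
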